## **10.2. ON STUDY EVALUATIONS**

The following procedures will be performed during the treatment period:

Weekly During Cycle 1:

- History
- Physical exam: vital signs
- Hematology: complete blood count, differential. If patient has Grade 4 neutropenia or thrombocytopenia, then CBC should be checked every 3-4 days until recovery to Grade 3.

- Serum Chemistry: ALT, AST, alkaline phosphatase, bilirubin, BUN, creatinine, electrolytes, calcium, magnesium, phosphorus, total protein, albumin, serum creatinine phosphokinase.
- Patient diary
- Assessing of AEs

Cycle 1 Day 11 ± 3 days

- FDG-PET

Cycle 1 Day 15 (up to day 28)

- Serum Pharmacodynamic and Immune Markers: Mandatory blood samples for pharmacodynamics, genomics and immune infiltrates
- Tumor Biopsy: Optional serum/tissue samples for pharmacodynamics, genomics and immune infiltrates

Prior to Subsequent Cycles\*

- History
- Physical exam: vital signs, height, weight, body surface area
- Performance status: Lansky/Karnofsky (Appendix I)
- Hematology: complete blood count, differential. If patient has Grade 4 neutropenia or thrombocytopenia, then CBC should be checked every 3-4 days until recovery to Grade 3.
- Serum Chemistry: ALT, AST, alkaline phosphatase, bilirubin, BUN, creatinine, electrolytes, calcium, magnesium, phosphorus, total protein, albumin, serum creatinine phosphokinase.
- Fasting glucose and Fasting serum lipid profile (triglycerides, total cholesterol, HDL and LDL). Fasting = 12 hours prior to glucose testing and lipid testing
- Serum or urine pregnancy: required for females of childbearing potential.
- Patient diary
- Assessing of AEs

Prior to Cycles 3, 5, 7 and then every 3 cycles (within 7 days prior to start of subsequent cycle)

- ctDNA blood sample
- Radiologic imaging: Evaluation of other measurable or evaluable disease sites by appropriate radiological evaluation (i.e. CT scan, MRI)

Prior to Cycles 2, 3, 5, 9, 13, and then every 6 cycles

- Patient reported pain severity and pain interference assessments.

Prior to Cycles 6 and 12, and then every 6 cycles (within 14 days prior to start of subsequent cycle)

- Echocardiogram or Cardiac MRI and ECG
- Ophthalmology evaluation: Particular emphasis will be given to the evaluation of corneal opacifications and retinal changes.

\*All evaluations can be obtained within 72 hours prior to start of a subsequent cycle, unless otherwise stated. All efforts should be made to adhere to the schedules listed. However, to provide flexibility to changes in patient's schedules and holidays for long term treatment, +/- 2 day changes will not be considered a protocol deviation and will not require reporting to IRB or FDA.

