### **Secondary Objectives**

- To define and describe the toxicities of selumetinib in combination with sirolimus in patients with unresectable or metastatic NF1 associated or sporadic MPNST.
- To assess the impact on pain intensity and pain interference and correlate to changes in clinical, imaging response and progression
- To assess progression free and overall survival

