## **Efficacy Evaluations**

- Response evaluation (RECIST) with appropriate imaging studies (MRI/CT) will be performed at baseline, prior to cycles 3, 5, 7 and then every 3 cycles (prior to cycles 10, 13, 16, etc.).

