### **1.2. Secondary Objective(s)**

- To define and describe the toxicities of selumetinib in combination with sirolimus in patients with unresectable or metastatic NF1 associated or sporadic MPNST.
- To assess the impact on intensity and pain interference and correlate to changes in clinical, imaging response and progression
- To assess progression free and overall survival

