#### End of Therapy

- History
- Physical exam: vital signs, height, weight, body surface area
- Performance status: Lansky/Karnofsky (Appendix I)
- Hematology: complete blood count, differential
- Serum Chemistry: ALT, AST, alkaline phosphatase, bilirubin, BUN, creatinine, electrolytes, calcium, magnesium, phosphorus, total protein, albumin, serum creatinine phosphokinase.
- Fasting\* glucose and Fasting serum lipid profile (triglycerides, total cholesterol, HDL and LDL) \*Fasting = 12 hours prior to glucose testing and lipid testing
- Patient diary

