## STUDY CALENDAR

Studies to be obtained	Pre-treatment 	During Cycle 1	Prior to subsequent cycles	End of therapy
History and Physical with vitals	X	Weekly	X	X
Performance status (Karnofsky)	X		X	X
CBC, differential	X	Weekly 	X 	X 
Serum Chemistry 	X	Weekly	X	X
Fasting glucose and serum lipid profile 	X		X	X
Urine or serum pregnancy  test	X		X	
Echocardiogram or cardiac MRI and ECG	X 		Prior to cycles 6 and 12, and every 6 cycles	
FDG-PET	X 	Day 11 +/- 3 days		
Ophthalmology Exam	X		Prior to cycles 6 and 12 and every 6 cycles	
Tumor Evaluation (by CT, MRI)	X 		Prior to cycles 3,5,7 and then every 3 cycles	
Patient reported pain	X		Prior to cycles 2, 3, 5, 9, 13, and then every 6 cycles	
Patient Diary		Weekly	X	X
Pharmacodynamic/Immune Markers 	X	Day 15 (up to day 28) 	ctDNA only: prior to cycles 3, 5, 7 and then every 3 cycles	
Tumor biopsy 	X	Day 15 (up to day 28) 		
Genomic testing 	X	Day 15 (up to day 28) 		

 See Section 3.2

For patients who experience Grade 4 ANC or platelets, check CBC q 3-4 days until  $\geq$  Grade 3

Sodium, potassium, chloride, bicarbonate, calcium, phosphorus, magnesium, creatinine, glucose, blood urea nitrogen, total protein, SGOT (AST), SGPT (ALT), total bilirubin, alkaline phosphatase, uric acid.

Fasting = 12 hours prior to testing. Glucose and serum lipid panel (triglycerides, total cholesterol, HDL, LDL)

 For females of child-bearing potential

Can be done within 4 weeks prior to enrollment.

 For serum and/or tissue samples, See Section 2.5

 Tumor biopsy is optional and will be collected only for patients who provide written consent and has tumor accessible to percutaneous biopsy

 Baseline blood will be (mandatory) collected and for patients who provide written consent and has tumor accessible to percutaneous biopsy may be collected at baseline and day 15 per patient consent

 Will be collected during cycle 1 on any one day on or after day 15 (i.e. one day between day 15-28)

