### **13.4. Analysis of Secondary Endpoints**

Summary statistics will be used to describe the study population and baseline characteristics.

Progression free survival will be determined using the Kaplan-Meier method, with PFS at important time points (6 or 12 months for example) reported along with 95% two sided confidence intervals.

Toxicities to be summarized descriptively and tabulations on the type, severity, and relationship to study treatment will be performed.

Changes in FDG-PET avidity, tumor biomarkers, pain severity and pain interference ratings, and immune markers will be exploratory and summarized using descriptive statistics and when feasible compared using Wilcoxon rank test or pairwise t-test. Correlations to imaging response, toxicity, and immune markers will be made if feasible.

The comprehensive genomic analyses including next generation sequencing and ctDNA analysis will be performed in the Oncogenomics laboratory ([name]/NCI). Bioinformatics analysis will be primarily performed at the NCI using well-established pipelines previously developed.

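### No pain form is scheduled at end of therapy or with the scans before cycles 7, 10, 16 and 22, which weakens the secondary objective of relating pain to imaging response and progression

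*Combined protocol and SAP*

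**What the plan says.** The Synopsis lists as a secondary objective "To assess the impact on pain intensity and pain interference and correlate to changes in clinical, imaging response and progression". Section 1.2 repeats it almost word for word.

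Pain is measured at baseline and then, in section 10.2, "Prior to Cycles 2, 3, 5, 9, 13, and then every 6 cycles". The Study Calendar, section 2.5.6, section 9.1.1.2 and the Synopsis list of mandatory correlative studies give the same cycles.

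The Synopsis (Efficacy Evaluations) places the scans "prior to cycles 3, 5, 7 and then every 3 cycles (prior to cycles 10, 13, 16, etc". Section 10.2 agrees ("Prior to Cycles 3, 5, 7 and then every 3 cycles") and allows imaging up to 7 days before the next cycle. Section 11.1 differs: it calls for re-evaluation before each odd-numbered cycle.

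The "End of Therapy" list in section 10.2 covers history, examination, performance status, laboratory tests and the diary, but no pain scale. The off-study list in section 10.3 adds imaging, again without pain. The pain row of the Study Calendar is empty in the end-of-therapy column.

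Section 13.4 treats pain ratings as exploratory. They are to be summarized descriptively and "when feasible compared using Wilcoxon rank test or pairwise t-test", with correlations to imaging response if feasible. It names no analysis of pain against progression.

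**The concern.** Progression is one of the events to which the objective relates pain, yet no pain form is tied to it. A progressing patient has a score at that moment only if the progression coincides with a scheduled form. Section 2.5.6 presents pain as a possible surrogate for tumor response and clinical benefit, so the score around progression is among the most informative for that question. A score not collected then cannot be recovered afterwards. With at most 21 patients, a handful of missing scores matters even for a descriptive analysis.

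**Working it through.** The plan gives no figure for this point, so there is none to reproduce. The check compares the two schedules and then weights the mismatch by when patients are likely to progress.

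**1. Schedules side by side (section 10.2)**

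- Pain forms before cycles: 2, 3, 5, 9, 13, 19, 25, ...
- Scans before cycles: 3, 5, 7, 10, 13, 16, 19, 22, 25, 28, ...
- Both: 3, 5, 13, 19, 25, ...
- Scan without pain form: 7, 10, 16, 22, 28, ...
- Pain form without scan: 2 and 9

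Through cycle 19, 4 of 7 scans are paired. For the scan before cycle 7 the latest score is two cycles old (8 weeks). For the scan before cycle 10 it is one cycle old (4 weeks), and before cycle 16 three cycles old (12 weeks).

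**2. Share of progressions first seen at an unpaired scan**

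Assumptions: exponential time to progression with median m months; every progression is found at a scheduled scan; no dropout; 28-day cycles without delay. The range for m comes from the documents. Table 1 gives 1.7 months for sorafenib and 13 weeks (about 3 months) for alisertib. Section 2.1.3 gives a median under 2 months across earlier trials. The Synopsis estimates a median treatment duration of 6 months, which is used here as if it were time to progression.

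The scan before cycle c falls at t(c) = 28(c - 1)/30.44 months. With rate L = ln 2 / m, the share first seen there is exp(-L t(previous scan)) - exp(-L t(c)).

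For m = 2, L = 0.3466. The proportions still progression-free at the scans before cycles 5, 7, 10, 13 and 16 are 0.2794, 0.1476, 0.0567, 0.0218 and 0.0084. The unpaired scans then contribute:

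- cycle 7: 0.2794 - 0.1476 = 0.132
- cycle 10: 0.1476 - 0.0567 = 0.091
- cycle 16: 0.0218 - 0.0084 = 0.013
- cycle 22 and later unpaired scans: about 0.002

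The total is 0.238. By the scan before cycle 5, 1 - 0.279 = 72% have progressed, all at scans that nominally have a form.

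| Median (months) | Progressed by pre-cycle-5 scan | First seen at unpaired scan | Of 21 patients | Unpaired under section 11.1 schedule |
|---|---|---|---|---|
| 1.7 | 78% | 20% | 4.1 | 15% |
| 2 | 72% | 24% | 5.0 | 19% |
| 3 | 57% | 33% | 6.9 | 27% |
| 6 | 35% | 43% | 9.1 | 41% |

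The counts assume that all 21 patients are enrolled and progress. Under the odd-cycle wording of section 11.1 the unpaired scans are those before cycles 7, 11, 15, 17 and so on, and 5 of 9 scans through cycle 19 are paired.

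**3. Two gaps that the model leaves out**

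- Section 5.5 ends therapy for clinical as well as radiographic progression, and section 7.1.1.6 recognizes progression shown by symptoms alone. A patient who stops this way between forms goes to an end-of-therapy visit with no pain scale.
- Paired scans are not fully secure. A scan may precede the next cycle by up to 7 days, whereas other evaluations may be done within 72 hours of it, and section 5.2 requires at least stable disease for that cycle to start. If the scan shows progression, the cycle never begins, and nothing says whether its pre-cycle form is still completed.

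Both can only raise the number of progressions without a score. The documents give no basis for a figure.

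**The case against.** The strongest counter-argument is that early progression works in the plan's favor. The first two on-study scans both have a scheduled form and another form precedes cycle 2, so in a disease that progresses as fast as section 2.1.3 describes, most progressions fall at paired scans. This stands. A reader might infer from the schedule that the objective cannot be met; the table does not support that. Nor is the raw count of paired scans a patient-weighted measure, since few patients reach the later scans.

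A reader might also take the 30% target benefit rate to mean that the other 70% have no pain score at progression. The 70% are patients without clinical benefit, and many of them would be imaged before cycle 3 or 5, where a form is scheduled.

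A third tempting inference is that change from baseline becomes a survivor comparison favoring the treatment. That is plausible for the forms from cycle 9 on, which are given only to patients still on treatment. The documents allow no estimate of its size, and they do not say that forms are skipped at progression.

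Finally, section 13.4 calls the pain analysis exploratory and no decision rule uses it. The schedule is repeated consistently, so it looks deliberate. This limits the stakes but does not remove the mismatch with an objective listed as secondary.

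**Conclusion.** The point holds as a weakness in data collection. Pain is not scheduled at end of therapy or with the scans before cycles 7, 10, 16 and 22. Under exponential progression found only at scheduled scans, about 20-24% of progressions would first be seen without a concurrent form at medians of 1.7 to 2 months, and about 43% if the 6-month treatment estimate stands for time to progression. That is roughly 4 to 9 of 21 patients. The section 11.1 scan schedule gives 15% to 41%, so the conclusion does not depend on which schedule is meant. The missing end-of-therapy form is the more serious gap, because it also leaves clinical progression uncovered. Pain change can still be related to imaging response at the paired scans, and the primary endpoint is untouched. This is a cheap improvement, not a defect that threatens the trial.

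**What to change.** - Give the existing single-page NRS-11 and PROMIS form at every tumor-evaluation visit, whether or not the next cycle starts, and at end of therapy.
- Update the Synopsis (Mandatory Correlative Studies), sections 2.5.6 and 9.1.1.2, the on-study and end-of-therapy lists in section 10.2, and the Study Calendar to match.
- Reconcile the scan schedule in section 11.1 with section 10.2 and the calendar.
- Add to section 13.4 a descriptive summary of change in pain from baseline to the progression or end-of-therapy form, by response status.

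With forms at every scan, all 7 scans through cycle 19 are paired and, under the assumptions above, the share of progressions at unpaired scans falls to zero. The end-of-therapy form covers clinical progression between scans.

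On the section 10.2 schedule, a patient treated through the scan before cycle 19 would complete at most three extra scan forms (before cycles 7, 10 and 16) and one at end of therapy: 4 x 5 = 20 minutes in all. History and examination already take place before each cycle and at end of therapy, so no new visit should be needed. The remaining cost is a small amendment with its usual approvals. Sample size and primary analysis do not change.

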### 2.1.3. Current Treatment for MPNST

The only known curative approach to MPNST is complete surgical resection with wide negative margins [3, 5]. Thus, the early diagnosis of MPNST is crucial, which may be difficult for NF1 patients for the reasons stated above. Adjuvant radiotherapy is recommended to improve local control in intermediate and high-risk lesions >5cm after marginal excision, but extremely high doses are needed and the local control rate is only 30-60% [17-19]. A recent prospective study evaluated the role of standard chemotherapy (doxorubicin, ifosfamide, and etoposide) in high grade unresectable MPNST (SARC006). Patients were stratified by sporadic vs. NF1-associated MPNST with the primary endpoint of determining objective response (CR or PR) after 4 cycles of chemotherapy. Local control with surgery and/or radiation followed with additional cycles of adjuvant chemotherapy. The objective response rate was lower in 17.2% in NF1 associated compared to 33% in sporadic, similar to what has been seen in retrospective reviews [3, 12]. In addition to objective responses, disease stabilization was achieved in most patients.

With increasing understanding in the molecular pathogenesis of MPNST, clinical trials of targeted agents have become available. Several histology specific trials with targeted agents have been performed for MPNST (Table 1). Although the trials that have been completed have not resulted activity in MPNST, they demonstrated that MPNST are aggressive cancers with rapid disease progression (median time to progression of <2 months) and that timely completion of trials for this rare malignancy is feasible.

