## **2.4. Study Design**

### **2.4.1. Overall Trial Design**

A Simon's two-stage phase 2 trial of MEK inhibitor selumetinib in combination with the mTOR inhibitor sirolimus to determine the safety and clinical benefit in patients with unresectable or metastatic MPNSTs. Both agents will be given orally on an empty stomach. Selumetinib will be given orally at a dose of 50mg by mouth twice daily continuously. This is the recommended dose in combination studies of selumetinib with mTOR inhibition. Sirolimus will be given orally at a dose of 4mg by mouth once daily with a cycle 1 day 1 loading dose of 12mg. Each cycle will be considered 28 days. Refer to section 13 for statistical design.

FDG-PET will be obtained at baseline prior to therapy and on day 11 (+/-3 days) to assess for early FDG-PET response. Disease status will be evaluated using standard imaging techniques (CT/MRI) prior to cycles 3, 5, 7 and then every 3 cycles (prior to cycles 10, 13, 16, etc) using RECIST criteria.

All patients (i.e. inaccessible lesions) will participate in blood collection only prior to therapy and one day (ranging from day 15 to day 28) during cycle 1 for pharmacodynamics, genomic, and immune markers.

Patients who have MPNST that are accessible to percutaneous interventional radiological (IR) guided biopsy will have option to participate in tumor biopsy collection prior to therapy and one day (ranging from day 15 to day 28) during cycle 1 for the pharmacodynamics, genomic, and immune markers.

All patients on study will be closely monitored for the development of toxicity including regular physical examinations, laboratory evaluations, echocardiograms, and ophthalmology exams.

Patients will be able to remain on treatment as long as they do not experience progressive disease or unacceptable toxicity.

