### 5.2. Criteria to start subsequent cycles

(Refer to section 6 for dose modifications)

A cycle may be repeated every 28 days if the patient has at least stable disease, has again met the ANC, platelet, hepatic, and renal function defined in Section 3.1, and has not met one of the off protocol therapy or off study criteria in Section 5.6 and 5.8. Up to 21 days (to day 49) will be allowed between cycles for recovery without modifying drugs on subsequent cycles if toxicity did not meet criteria requiring dose modification.

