#### 5.4.10. Management of asymptomatic left ventricular ejection fraction (LVEF) reduction

Abbreviations: LVEF, Left ventricular ejection fraction; LLN, lower limits of normal

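### Scheduled cardiac and eye exams reach only patients still on treatment late in cycle 5, so asymptomatic LVEF, QTcF and retinal findings need the number examined as their denominator

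*Combined protocol and SAP*

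**What the plan says.** Section 2.4.1 states: "All patients on study will be closely monitored for the development of toxicity including regular physical examinations, laboratory evaluations, echocardiograms, and ophthalmology exams". Section 10.2 gives the timing of the echocardiogram or cardiac MRI, the ECG and the ophthalmology evaluation as "Prior to Cycles 6 and 12, and then every 6 cycles (within 14 days prior to start of subsequent cycle", and the Study Calendar agrees: "Prior to cycles 6 and 12, and every 6 cycles". The "End of Therapy" list, the off-study list in section 10.3 and the end-of-therapy column of the calendar contain none of the three.

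On staying on treatment, section 5.2 says: "A cycle may be repeated every 28 days if the patient has at least stable disease". Section 5.5 ends protocol therapy at progression. Scans are due before cycles 3, 5 and 7. Section 13.1 counts CR, PR, or SD lasting at least 4 cycles as clinical benefit.

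On reporting, section 13.4 says: "Toxicities to be summarized descriptively and tabulations on the type, severity, and relationship to study treatment will be performed". Section 11.1.1 counts a patient in the toxicity evaluation after one dose plus either a toxicity or a completed first cycle. Neither section asks for a post-baseline cardiac or eye exam. Section 5.4.10 is headed "Management of asymptomatic left ventricular ejection fraction (LVEF) reduction".

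**The concern.** Describing the toxicities of the combination is a secondary objective. The protocol treats the heart and retina as organs of interest: section 3.1.13 sets ejection fraction and QTcF limits for entry, section 3.2.6 excludes prior retinal detachment or vein occlusion, and section 7.3.1 lists reduced LVEF and retinal vein occlusion. An asymptomatic change in LVEF, QTcF or the retina is found only if someone looks. Under the schedule, nobody is due to look until a patient has had almost five cycles.

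If such findings are tabulated over the whole toxicity-evaluable set, a patient who was never examined counts the same as one examined and found normal. The examined patients are also those who stayed on longest, so those who stopped early, including for intolerance, are under-represented. The table would then look more reassuring and more precise than the data allow.

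**Working it through.** **Inputs.** Cycle of 28 days (section 5.1); exam window 14 days (10.2); p0 = 0.05, p1 = 0.30, stages of 7 and 21 (13.1); median treatment duration 6 months (synopsis, Anticipated Length of Study); historical medians of under 2 months (2.1.3) and of 1.7 months and 13 weeks (Table 1); reduced LVEF 2.0% of 355 on selumetinib (7.3.1).

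**1. The design's own figures.** Early termination under p0 is 0.95^7 = 0.698, and expected N is 7 + 14 × (1 − 0.698) = 11.2. Both match section 13.1. The probability of declaring activity is 0.064 at p0 and 0.904 at p1, within the stated limits.

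**2. Timing.** 5 × 28 = 140 days and 140 − 14 = 126, so the first window is about days 126 to 140 if no cycle is delayed.

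**3. The bound.** To be in cycle 5 a patient must have passed the pre-cycle-5 scan with SD or better. Reading SD at that scan as SD for 4 cycles, the patient is already a success on the primary endpoint. Hence the share with a scheduled exam is at most the clinical benefit rate. It can be lower, because a patient with benefit may stop before the window.

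**4. Share with no scheduled post-baseline exam.** The exponential rows use 1 − 0.5^(t/median).

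| Basis | Share with none |
|---|---|
| p1 = 0.30 | at least 70% (14.7 of 21) |
| p0 = 0.05 | at least 95% |
| Median 6 months (182.6 days) | 38% at day 126; 1 − 0.5^(140/182.6) = 41% at day 140 |
| Median 13 weeks | 1 − 0.5^(140/91) = 66% at day 140 |
| Median 2 months | 76% at day 126; 80% at day 140 |
| Median 1.7 months | 1 − 0.5^(140/51.7) = 85% at day 140 |

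The 5% is a rate per patient and should not be read as 1 of 21. Under p0 the trial stops at 7 with probability 69.8%, with no patient having benefit. If it reaches 21, expected successes are 0.35/0.302 + 14 × 0.05 = about 1.9.

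**5. The protocol's figures disagree.** Without cycle delays, a 6-month median means at least half of patients are on treatment past day 140, hence a benefit rate of at least 50% against a target of 30%. Conversely, exponential time on treatment with 30% remaining at 4 cycles (112 days, 3.68 months) implies a median of 3.68 × ln 0.5 / ln 0.30 = 2.1 months.

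**6. Dilution.** For a finding that only an exam can show, tabulated rate = true rate × share examined. The 10% rate is an assumption.

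| True rate | 5% examined | 30% examined | 59% examined |
|---|---|---|---|
| 2.0% | 0.1% | 0.6% | 1.2% |
| 10% | 0.5% | 3.0% | 5.9% |

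In 21 patients, the chance of seeing no case at a true 10% is 53% with 30% examined, 28% with 59% examined, and 0.90^21 = 11% with all examined.

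**7. Apparent precision.** With no events, the upper limit of the two-sided 95% exact interval is 1 − 0.025^(1/n). For n = 21 it is 16%. For n = 12 (0.588 × 21 = 12.3) it is 26%, and for n = 6 (0.30 × 21 = 6.3) it is 46%.

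**The case against.** A reader might infer that 70–95% of patients will go unexamined and that cardiac and retinal harm will be reported as near zero over all treated patients. The documents do not support that.

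- The 5% and 30% rates are hypotheses for a test, not forecasts of time on treatment. The protocol's only forecast is the 6-month median, under which at most half lack a scheduled exam if cycles are not delayed. This stands, and it is why the range starts near 40%. However, that forecast conflicts with the design rates and with the history in section 2.1.3: "MPNST are aggressive cancers with rapid disease progression (median time to progression of <2 months".
- History, physical examination and adverse-event assessment are scheduled weekly in cycle 1 and before every later cycle. Symptomatic cardiac or visual events can surface there, so only asymptomatic findings are affected. This stands.
- Sections 5.4.10 and 5.4.11 are available here only as headings and abbreviations. They may call for triggered exams, so unscheduled exams cannot be ruled out. This stands.
- Section 13.4 names no LVEF, QTcF or retinal rate and plans no interval for toxicity. The dilution follows from using the section 11.1.1 set as denominator, which is the natural reading but is not spelled out for exam findings. The limits in step 7 illustrate precision and are not planned analyses.
- At the only documented LVEF rate, 2.0%, zero cases in 21 has probability 0.98^21 = 65% even if everyone is examined. A zero would therefore be unsurprising under any schedule. This stands, and it is a reason to show how many were examined.
- Exams before cycles 6 and 12 can be called regular, so section 2.4.1 is not flatly contradicted. But that section refers to all patients, and the schedule provides no on-treatment exam for those who stop before the first window.

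**Conclusion.** The point holds as a matter of reporting. No cardiac or eye exam is scheduled between baseline and about days 126 to 140, or when therapy ends, and the share of patients with a scheduled post-baseline exam cannot exceed the clinical benefit rate. The share without one runs from roughly 40% (6-month median, exponential time on treatment, no cycle delays) to at least 70% at p1 and at least 95% at p0. The width of that range reflects a disagreement within the protocol that needs resolving.

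Tabulated over the toxicity-evaluable set, rates of asymptomatic LVEF, QTcF and retinal findings shrink to the share examined times the true rate. Whether the result is near zero depends on a true rate that the documents do not give for this combination. The conclusion assumes few unscheduled exams; each one narrows the gap. Section 7.2.1 makes adverse-event reporting mandatory only from grade 3, so lower-grade exam findings may not reach the adverse-event table at all. That is a further reason to report exam results directly.

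**What to change.** In section 13.4, keep the standard adverse-event table over toxicity-evaluable patients. Add a separate summary of LVEF, QTcF and ophthalmology exam findings over patients with at least one post-baseline exam of that type, scheduled or unscheduled. Show that number beside the number treated, and give an exact confidence interval for each proportion. This costs a few lines of text and a check that the eCRFs hold the exam dates and results. The intervals will be wider, which is the honest precision.

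Separately, the sponsor should reconcile section 2.4.1 with section 10.2, the end-of-therapy list, section 10.3 and the Study Calendar, and reconcile the 6-month median in the synopsis with the rates in section 13.1. Whether and when to examine patients who stop before cycle 6 is the sponsor's clinical decision. Any added exams would carry their own cost. The reporting change is useful whatever is decided.
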